14.5 Method of Analysis

The best overall response is the best response recorded from the start of treatment until progression/recurrence (taking as reference for progressive disease the smallest measurements recorded since the treatment started), and is the best overall response rate at any response assessment timepoint (see Appendix 5). Objective response rates will be described for patients assigned to each treatment arm as long with exact 95% confidence intervals.

Progression-free survival, and overall survival will be calculated from the start of treatment by using the Kaplan-Meier method along with 95% confidence intervals. Patients' withdrawals from interventions for reasons other than progression or death will be treated as independent censoring, and sensitivity analyses will be conducted as described in 14.4

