10.4 Post-Treatment Evaluations

Patients who discontinue study treatment for reasons other than PD (e.g., toxicity) should continue to undergo the full tumor assessment 6–8 weeks after study treatment is discontinued and

every six months thereafter until the patient dies, experiences PD, withdraws consent, or until the study closes, whichever occurs first. Patients who start a new anticancer therapy in the absence of PD should continue to be followed for progression according to the protocol schedule unless consent is withdrawn, the patient dies, or the study closes, whichever occurs first.

For patients who experience PD or who discontinue the study treatment due to an AE or SAE, full tumor assessment should be obtained within 30 days after the last dose of study treatment or before another anticancer therapy is initiated. Additional required tests for these patients are outlined in Appendix 1.

Patients that drop out prior to evaluation due to PD, AE, SAE will be assessed for survival and toxicity every 3 months until the start of new anti-lymphoma therapy.

Female patients of reproductive potential who are not surgically sterile must practice adequate birth control for a minimum of twelve months post-treatment; male patients who are not surgically sterile must practice adequate birth control for a minimum of three months post-treatment.

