10.5 Survival and Subsequent Anticancer Therapy

Survival follow-up information will be collected via telephone calls, patient medical records, and/or clinic visits approximately every 3 months until death, loss to follow-up, or study termination by the funding source of Principal Investigator. All patients who have discontinued treatment without disease progression will undergo all follow-up exams noted in Appendix 1 during follow-up. All other patients will be followed for survival and new anticancer therapy information only, unless the patient requests to be withdrawn from follow-up (this request must be documented in the source documents and signed by the investigator). If the patient withdraws from study treatment but not from follow-up, the study staff may use a public information source (e.g., county records) to obtain information about survival status only.

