14.4 Secondary Efficacy Variables

PFS is defined as the time from the first day of study treatment to PD or death, whichever occurs first. If a patient is alive and has not experienced PD, PFS will be independently censored at the day of the last tumor assessment. Patients with no post-baseline tumor assessments will be included in the PFS analysis but censored at the start of treatment.

OS is defined as the time from the first day of study treatment to death from any cause. For OS, patients without a date of death will be independently censored on the date a patient was last known to be alive.

Incidence of toxicity and adverse events will be summarized by frequencies and percentages for each of the two cohorts.

Patients with early withdrawal from the study will be considered as independently censored according to previous paragraphs. However, the censoring may be related to the disease status and therefore not independent. Therefore, sensitivity analyses will be conducted where these patients will be counted as events.

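### Section 14.5 makes withdrawal from the intervention a censoring event for PFS and OS, which conflicts with 14.4 and, read literally, leaves observed progressions and deaths unused

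*Combined protocol and SAP*

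**What the plan says.** **Section 14.4** sets the endpoints: "PFS is defined as the time from the first day of study treatment to PD or death, whichever occurs first". On censoring it says: "If a patient is alive and has not experienced PD, PFS will be independently censored at the day of the last tumor assessment". A patient with no post-baseline assessment is censored at the start of treatment. OS runs to death from any cause, with censoring at the date last known alive. On withdrawal: "Patients with early withdrawal from the study will be considered as independently censored according to previous paragraphs". It then concedes that such censoring may be related to disease status, and so "sensitivity analyses will be conducted where these patients will be counted as events".

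**Section 14.5** names the estimator: "Progression-free survival, and overall survival will be calculated from the start of treatment by using the Kaplan-Meier method". It adds: "Patients' withdrawals from interventions for reasons other than progression or death will be treated as independent censoring", and refers to 14.4 for the sensitivity analyses. It gives no censoring date.

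**Section 10.4** covers follow-up after stopping: "Patients who discontinue study treatment for reasons other than PD (e.g., toxicity) should continue to undergo the full tumor assessment". These scans come at 6-8 weeks and then every six months, until progression, death, withdrawn consent or study closure. Patients who start new therapy without progression are still followed for progression. A separate sentence limits patients who drop out before evaluation to survival and toxicity checks every 3 months until new therapy.

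**Section 10.5** adds: "All patients who have discontinued treatment without disease progression will undergo all follow-up exams noted in Appendix 1 during follow-up". Survival is collected about every 3 months until death, loss to follow-up or study termination.

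**The concern.** The two statistics sections use different triggers. Section 14.4 acts on leaving the study; 14.5 acts on leaving the intervention. A patient who stops drug for toxicity and stays in follow-up falls under 14.5 but not under the 14.4 withdrawal rule.

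Take a patient who stops at Cycle 6 (5 × 21 = 105 days, about 3.5 months) and has documented progression at month 14. Under 14.4 this is an event at month 14. Under a literal 14.5 it is a censored time at about month 3.5, and the sensitivity analysis makes it an event at about month 3.5. For OS, a death after the stop would be censored in the main analysis, and a patient known to be alive could be counted as dead in the sensitivity analysis.

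Both secondary efficacy endpoints therefore have two possible censoring rules. The same PFS and OS data also feed the biomarker logrank comparisons in 14.6.

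**Working it through.** **No plan figure to reproduce.** The documents state no PFS or OS median, event count or power. The primary rule (9 or more responders of 25) has exact type 1 error 0.047 at 20% and power 0.818 at 43%, consistent with 14.1. It does not involve censoring.

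**Which reading fits the text.** Section 4.2 uses *intervention* for atezolizumab with or without radiotherapy. Section 10.5 distinguishes withdrawing from study treatment from withdrawing from follow-up. Sections 13.1 and 13.2 deal separately with leaving the study and stopping treatment. These favour the literal reading. Against it, 14.5 refers back to 14.4 for its sensitivity analyses and gives no date of its own. The documents do not settle the matter.

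**Size under the literal reading.** All inputs are assumptions, apart from the 24-month horizon, which echoes the 2 years in 10.6:
- exponential PFS with median 9 months, so h = ln 2 / 9 = 0.0770 per month;
- a share p of patients prone to a stop without progression, at a time uniform over months 1-6;
- these patients progress at k times the rate of the others throughout;
- G(t), the probability of not yet having stopped: 1 before month 1, (6 − t)/5 from month 1 to month 6, and 0 afterwards.

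The three analyses estimate:
- all follow-up used (14.4): S(t) = (1 − p)e^(−ht) + p e^(−kht);
- censored at stop (14.5, literal): the curve with hazard h[(1 − p)e^(−ht) + kp e^(−kht)G(t)] / [(1 − p)e^(−ht) + p e^(−kht)G(t)], integrated numerically;
- stop counted as event (sensitivity): S(t) = (1 − p)e^(−ht) + p e^(−kht)G(t).

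The share of events lost is p × mean over s in 1-6 of [e^(−khs) − e^(−24kh)], divided by (1 − p)(1 − e^(−24h)) + p(1 − e^(−24kh)).

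Worked case, p = 0.2 and k = 1:
- The mean of e^(−hs) is (0.9259 − 0.6300)/(5 × 0.0770) = 0.768.
- Lost events are 0.2 × (0.768 − 0.157) = 0.122 per patient, against 0.843 in total, or 14.5%.
- In 25 patients that is about 3.1 of 21.1 events.
- The sensitivity median solves 0.8e^(−ht) = 0.5, so t = ln 1.6 / h = 6.10 months.

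Median PFS in months:

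| p | k | all follow-up | censored at stop | stop as event | events lost |
|---|---|---|---|---|---|
| 10% | 1 | 9.00 | 9.00 | 7.63 | 7.3% |
| 10% | 1.5 | 8.63 | 8.83 | 7.63 | 7.2% |
| 10% | 2 | 8.37 | 8.69 | 7.63 | 6.7% |
| 20% | 1 | 9.00 | 9.00 | 6.10 | 14.5% |
| 20% | 1.5 | 8.27 | 8.66 | 6.10 | 14.3% |
| 20% | 2 | 7.77 | 8.36 | 6.10 | 13.2% |

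Simulating 400,000 patients per scenario gives the 20% medians to within 0.03 months.

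**Second set of assumptions.** Take median PFS 6 or 12 months, 10-30% stopping for toxicity by month 12, hazard after the stop 1-3 times higher, and 24 months of follow-up. Censoring at stop then loses 1.2 to 5.3 PFS events per 25-patient arm. With unchanged hazard, 12-month PFS is unaffected. With hazard 2-3 times higher it is overstated by about 1 to 7 points. In the most extreme case the three analyses give 42.9% (all follow-up), 50.1% (censored) and 35.1% (stop as event).

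**The case against.** **Section 14.5 may be a loose restatement of 14.4.** It sets no censoring date, and 14.4 sends withdrawn patients back to its own rules. Section 13.1 mixes the terms by sending patients who withdraw from the study to the assessments in 10.3-10.5, and toxicity stops are usually called discontinuations. On that reading the month-14 progression counts and nothing is lost. This stands. A reader might infer that the plan certainly discards events; the text supports that only conditionally.

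**The plan already has a worst-case check.** A reader might infer that counting stoppers as events cannot bracket the true value. The table shows otherwise: with k of 1.5 or 2 the full-follow-up median lies between the two planned analyses, and with k = 1 the main analysis is already right. What remains is that neither analysis estimates the full-follow-up value. The bracketing is also not general: if patients who stop did better than others, that value would lie above both.

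**The effect is small against the precision of 25 patients.** With p = 20% and k = 1.5, the median from 25 patients has a 95% sampling range of about 4.5 to 14 months. This stands, but it does not justify leaving two rules in place.

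**Follow-up is not complete for everyone.** The 10.4 sentence on drop-outs before evaluation and the end of follow-up at consent withdrawal in 13.1 both limit what is observed. The first on-treatment scan is at C5D1 (4 × 21 = 84 days, about 2.8 months), so some early stops precede it. The loss in the table is therefore nearer an upper figure for its assumptions.

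**Conclusion.** The conflict between 14.4 and 14.5 is real and should be corrected before analysis. Loss of observed events follows from the literal wording of 14.5 and is not certain. Under that reading and the 9-month illustration:
- 10-20% of patients prone to stop costs roughly 7-15% of PFS events;
- median PFS is unbiased if their progression rate equals that of the others;
- with 20% prone to stop, the median is overstated by about 0.4-0.6 months at 1.5-2 times the rate (0.2-0.3 months with 10%).

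These figures rest on assumed medians, stop rates and hazards, ignore scan intervals, and assume complete follow-up after the stop.

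A reader might also infer that the comparison between arms or the trial's main decision is compromised. The documents do not support this. Section 14.1 analyses each arm separately, PFS and OS are descriptive secondary endpoints with no planned test between arms, and the 9-of-25 response rule does not use them.

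**What to change.** In 14.5, replace the reference to withdrawal from interventions with *withdrawals from study follow-up (consent for follow-up withdrawn or lost to follow-up)*. Add that stopping study treatment is not a censoring event and that all later progressions and deaths count under 14.4. Limit the count-as-event sensitivity analysis to patients who leave follow-up. If censoring at treatment stop is of interest, keep it only as a labelled sensitivity analysis.

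The cost is a few sentences in 14.5. No new assessments are needed, because 10.4 and 10.5 already provide the follow-up for most of these patients.

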14.6 Method of Analysis for Correlative Endpoints

Objective response rates, progression-free survival, and overall survival will be estimated for patients with preexisting tumor antigen restricted tumor infiltrating lymphocytes (TILs) and patients without preexisting tumor antigen restricted (TILs), and for patients who demonstrate a 2-fold expansion of T cell receptor (TCR) clonality and patients who do not demonstrate a 2-fold expansion of TCR clonality, and groups will be compared using Fisher's exact tests (ORR) and logrank tests (PFS and OS). Similar comparison will be performed to associate other biomarkers described in 2.3

with the outcomes. To assess the impact of treatment on peripheral blood cytokine/chemokine levels, Wilcoxon signed rank test will be used to test the intra-patient changes in these factors.

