10.1 Laboratory/ Pathology Assessments

Samples for hematology, serum chemistries, coagulation, urinalysis, and the pregnancy test will be analyzed at the study site's local laboratory. Analysis of biomarkers on tumor and blood samples will be performed on site. Refer to section 12.2 and Appendix 9 for correlative studies workflow.

The following assessments will be performed at Memorial Sloan-Kettering Cancer Center:

Baseline tumor biopsy

- All patients will undergo a baseline tumor biopsy sample collection within 30 days of registration.
 - If the patient has recently undergone a biopsy and has not received any intercurrent anti-lymphoma therapy, archival tissue can be used

- Acceptable samples include core needle biopsies for deep tumor tissue or lymph nodes or excisional, incisional, punch, or forceps biopsies for cutaneous, subcutaneous, or mucosal lesions.
- Every intention should be made to collect the pre treatment biopsy from the same site that will be radiated. The on protocol biopsy should be in the same location unless clinically unfeasible or not in the interest of the patient's safety.

On-treatment tumor biopsy

- All patients will undergo an on-treatment tumor biopsy sample collection, if clinically feasible, during Cycle 2 (as per study flowchart in Appendix 1).
- Acceptable samples include fine needle aspirations or core needle biopsies for deep tumor tissue or lymph nodes or excisional, incisional, punch, or forceps biopsies for cutaneous, subcutaneous, or mucosal lesions. Core needle biopsies are preferred.
- The tissue will be used for correlative investigations.

Tumor biopsy at the time of initial radiographic progression (This tumor biopsy is **optional** based on whether it is feasible to obtain enough tissue at the site and therefore, 'clinically indicated/feasible', and not optional for the patient to choose whether or not they want one for the study)

- Patients may undergo a tumor biopsy sample collection, if clinically feasible, at the first evidence of early radiographic disease progression (i.e., not preceded by meaningful tumor regression). Biopsy at time of initial radiographic progression is recommended but not mandatory.
- Acceptable samples include fine needle aspirations or core needle biopsies for deep tumor tissue or lymph nodes or excisional, incisional, punch, or forceps biopsies for cutaneous, subcutaneous, or mucosal lesions.

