12.2 Correlative Studies

12.2.1 Assessment of T-Cell Receptor Diversity/ Clonality

We will determine if clinical responses to atezolizumab are associated with preexisting tumor antigen restricted effector T cells or the development of a more clonal T-cell receptor (TCR) repertoire, and we will determine what impact the addition of concurrent local, low-dose radiotherapy has on TCR diversity and clinical responses.

TCR clonality evaluation: Flow-cytometry-sorted CD4+ and CD8+ T cells from both pre and on-treatment biopsies and peripheral blood mononuclear cells will be separated and DNA will be promptly extracted using a low-input DNA extraction kit (Qiagen). Clonal TCR diversity will be assessed using the Adaptive ImmunoSEQ kit. The resulting multiplexed PCR product will be sequenced on an Illumina MiSeq system and analyzed using the ImmunoSEQ analyzer. (Appendix 9)

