^c Sodium, potassium, chloride, bicarbonate, glucose, BUN, creatinine, calcium, total and direct bilirubin, total protein, albumin, ALT, AST, alkaline phosphatase, amylase, lipase, LDH, uric acid, magnesium, phosphorus.

^d Bone marrow biopsy and aspirate is required within 60 days of C1D1, provided no treatment has been administered in the interim. For patients with involvement of follicular lymphoma at baseline, repeat testing is required only to confirm CR or as clinically indicated.

^e Imaging and reporting requirements for tumor assessment is described in Appendix 5. Patients will require a PET scan with diagnostic quality CT CAP (with intravenous and oral contrast, unless contraindicated) at study screening, Cycle 5, and EOT. A baseline PET with diagnostic CT CAP scan is required within 45 days of C1D1. For patients who have had a PET scan performed within 45 days of C1D1, a simulation scan (PET, CT, or MRI) will only be done if the patient is randomized to Arm 2 (RT arm). For patients who have not had a PET scan within 45 days of C1D1, baseline PET imaging will be a PET-simulation scan.

^f Tumor biopsy is required in all patients within 45 days of C1D1. Tumor FNA or core biopsy is required in all patients at Cycle 2 Days 14-20 (core biopsy is preferred). Tumor biopsy is recommended at time of progression on study. Tumor biopsy should be outside the field of radiation to allow for an accurate assessment of systemic changes to the tumor microenvironment following local irradiation. Acceptable samples include core needle biopsies for deep tumor tissue or lymph nodes or excisional, incisional, punch, or forceps biopsies for cutaneous, subcutaneous, or mucosal lesions

^g Research blood samples will be collected for correlative investigations as outlined in Section 12.2 of the protocol. Additional information about the workflow for correlatives can be found in Appendix 9.

^h Only if randomized to low- dose radiotherapy arm

ⁱ T3 and T4 should be tested only if TSH is abnormal.

- ^j Labs can be done within 5 days of day 1 of each cycle.
- ^k Infectious disease testing includes: Epstein-Barr virus (EBV) serology (EBNA IgG), Hepatitis B virus (HBV) serology (HBsAg, antibodies against HBsAg, hepatitis B core antigen), HCV serology (anti-HCV), and HIV 1 & 2 antibodies. HBV DNA test is required for patients who have positive serology for anti-HBc. HCV RNA test is required for patients who have positive serology for anti-HCV.
- ^l Within 45 Days of C1D1

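### Section 14.6 compares PFS and OS from first treatment by a TCR-expansion status known only later, without a defining sample or a landmark, which permits guarantee-time bias favouring expanders

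*Combined protocol and SAP*

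**What the plan says.** Section 14.6 sets out the correlative comparisons. One grouping is by TCR clonality: "patients who demonstrate a 2-fold expansion of T cell receptor (TCR) clonality and patients who do not demonstrate a 2-fold expansion of TCR clonality". For each grouping, "groups will be compared using Fisher's exact tests (ORR) and logrank tests (PFS and OS").

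The time origin comes from Section 14.4: "PFS is defined as the time from the first day of study treatment to PD or death, whichever occurs first", and "OS is defined as the time from the first day of study treatment to death from any cause". Section 14.5 repeats it: "Progression-free survival, and overall survival will be calculated from the start of treatment by using the Kaplan-Meier method". Section 14.6 gives no other origin for the TCR comparison.

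Section 12.2.1 names the material for TCR clonality: "T cells from both pre and on-treatment biopsies and peripheral blood mononuclear cells will be separated". Appendix 1, footnote f, fixes one on-treatment tissue sample: "Tumor FNA or core biopsy is required in all patients at Cycle 2 Days 14-20". The research-blood row of the Appendix 1 flowsheet is marked at screening, Cycle 2, Cycles 3 to 17, follow-up and off treatment. Footnote g ties those draws to Section 12.2 as a whole.

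The plan does not say which sample defines expansion, whether one reading or any reading counts, or what happens to patients without a usable pair. Such patients are foreseeable. Section 10.1 makes the on-treatment biopsy subject to clinical feasibility and relaxes the fresh baseline requirement: "If the patient has recently undergone a biopsy and has not received any intercurrent anti-lymphoma therapy, archival tissue can be used".

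**The concern.** Patients are sorted by something that happens after the clock has started. To be called an expander, a patient must reach a post-baseline sample, so time before that sample is guaranteed event-free for expanders and not for the others. If several samples may count, a patient who stays on treatment longer also has more opportunities to cross the 2-fold threshold by chance. Both effects make expanders look better even when expansion has nothing to do with outcome.

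At stake is the interpretation of an exploratory finding. Section 2.3 opens with the question of whether responses are associated with pre-existing tumour-restricted T cells or a more clonal repertoire. A spurious PFS or OS advantage for expanders would look like mechanistic support for that idea. The companion comparison, by pre-existing tumour-restricted TILs, uses a baseline status and does not have this problem.

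**Working it through.** The plan gives no sample size, power or error rate for this comparison, so there is no figure of its own to reproduce.

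**Timing, from 21-day cycles.**
- Cycle 2 Days 14-20 are study days 21 + 14 = 35 to 21 + 20 = 41. The simulations use day 38.
- The first scheduled on-treatment response assessment in Appendix 5 is C5D1: 1 + 4 × 21 = day 85.
- Research blood in Cycles 2 to 17 allows up to 16 draws. By C5D1 there have been 4 (Cycles 2 to 5).

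**Chance of ever being called an expander.** Suppose any draw may count, each with chance q of a 2-fold reading unrelated to outcome, independently. After k draws the chance is 1 − (1 − q)^k.

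| q (assumed) | k = 4 | k = 16 |
|---|---|---|
| 2% | 7.8% | 27.6% |
| 5% | 1 − 0.95^4 = 18.5% | 1 − 0.95^16 = 56.0% |
| 10% | 34.4% | 81.5% |

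**Simulated false-positive rate for PFS.** Each setting uses 50 patients (both arms pooled), 2,000 trials, exponential PFS, expansion unrelated to PFS, and a two-sided 5% log-rank test from first treatment. Median PFS, q and correlation are assumptions; the documents give none of them.

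*A. Any blood draw in Cycles 2-17 before progression may count; q = 5%; progression read only at scheduled scans (days 85, 169, 253, 365, then about six-monthly). Correlated readings use a latent normal variable.*

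| Within-patient correlation | Median PFS 6 months | Median PFS 12 months |
|---|---|---|
| 0 | about 42% | about 25% |
| 0.5 | about 10-11% | about 7-8% |
| 0.8 | about 6% | about 4-5% |

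With independent readings nearly all rejections favour expanders, and the median hazard ratios are 0.53 and 0.63. If progression is instead observed continuously, independent readings at q = 5% give 62% and 42%.

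*B. Status from the single Cycle 2 biopsy only, with an assumed 40% expanding.*

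| Handling of patients who progress before day 38 | 6 months | 12 months | 18 months |
|---|---|---|---|
| Counted as non-expanders | 10.8% | 6.8% | 5.7% |
| Excluded, clock still from first treatment | 5.5% | 5.3% | 5.6% |
| Excluded, clock from day 38 (landmark) | 5.8% | 5.2% | 5.3% |
| Counted as non-expanders, but progression seen only at scheduled scans | 5.2% | 5.0% | 4.5% |

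With 2,000 trials the Monte Carlo standard error at 5% is √(0.05 × 0.95 / 2000) ≈ 0.5 percentage points, so the last three rows are compatible with the nominal level.

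**Landmark applied to repeated blood.** With status fixed by C5D1 (day 85), only patients event-free then, and time counted from then, rejection is 5.0-6.6% and the median hazard ratio 1.01-1.03.

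OS was not simulated. The same structure applies to it, but its size is not quantified here.

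**The case against.** The strongest reply is that Section 14.6 is merely underspecified. A reader might infer from the blood schedule that TCR status is read up to 16 times and that one positive reading is enough. The documents do not say that. Section 12.2.1 lists blood cells beside the pre- and on-treatment biopsies, only one on-treatment biopsy is scheduled, and the serial tubes also serve storage, flow cytometry and cytokine assays. A single pre/on-treatment pair is an equally natural reading, and under it the excess is small or absent. This stands.

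The independence assumption is also fairly challenged. Every reading is compared with the same baseline in the same patient, so correlation is expected, and the 25-42% range shrinks quickly once it is allowed for. That range belongs near the upper end, not at the centre.

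Three further inferences go beyond the text. First, nothing states that patients without a pair become non-expanders; the wording leaves it open. Second, Section 2.3 gives no timing for MRD, and for cytokines Section 14.6 specifies a within-patient signed rank test and no responder grouping, so neither can be called affected as written. Third, relapse biopsies, which Appendix 9 processes in the same way, give patients who progress an extra tissue sample, which pushes against the bias.

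Finally, the comparison is exploratory: the go/no-go rule and arm selection in Section 14.1 rest on response counts and toxicity. That limits the consequence. It does not supply the missing definition or time origin.

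**Conclusion.** The concern holds in a limited form. As written, Section 14.6 tests PFS and OS from first treatment by a post-baseline status, with nothing to prevent guarantee-time bias in favour of expanders. For PFS, the null rejection rate of a nominal 5% test is about 5-11% if only the Cycle 2 biopsy counts. If any blood draw may count, it runs from about 4-6% (correlation 0.8) through 7-11% (0.5) to 25-42% (independent readings), for median PFS of 12 to 6 months and a 5% chance per draw. These inputs are assumed, so the figures show direction and range, not a forecast.

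It would be too strong to say that longer PFS necessarily produces expander status; that depends on a definition the plan has not chosen. The primary conclusion is unaffected. The reason to act is that the definition could otherwise be settled after outcomes are known, and a safe version costs little.

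**What to change.** In Section 14.6:

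- Define expansion from one fixed pair per compartment: baseline versus the Cycle 2 Day 14-20 biopsy for tissue, and baseline versus the scheduled Cycle 2 research sample for blood. State the blood sampling day explicitly, because the flowsheet columns within Cycle 2 cannot be read reliably in the available text.
- For this comparison, start PFS and OS at the date of that on-treatment sample, and include only patients alive and progression-free then with both samples of the pair.
- Report patients without a pair as a separate group, with reasons, and not as non-expanders.
- Use later samples only as a time-dependent covariate.
- Apply the same landmark to any other post-baseline biomarker grouping tested against PFS or OS.

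The cost is wording: the samples are already scheduled. The downside is that early events and patients without a pair drop out of this exploratory comparison, which reduces an already small sample.
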